## 2.2 POTENTIAL RISKS AND BENEFITS

### 2.2.1 POTENTIAL RISKS

This treatment modality was designed to inherently minimize the risk to the subject. However, treatment with energy-based modalities (laser, radiofrequency, and plasma devices) produce subsequent heating of the soft tissue that could involve the following commonly Expected Treatment Effects (ETEs): discomfort/pain, edema, erythema, ecchymosis, hypoesthesia, temporary sensory nerve injury (touch sensitivity, itching, temporary numbness/tingling), transient migratory firmness, and temporary and/or transient crepitus.

In addition to commonly expected treatment effects, treatment with the Renuvion APR system could involve the following risks: helium embolism into the surgical site due to inadvertent introduction into the venous or arterial blood supply system, unintended burns (deep or superficial), pneumothorax, temporary or permanent motor nerve injury, ischemia, fibrosis, infection, gas buildup, bleeding, hematoma, seroma, subcutaneous induration, pigmentation changes, increased healing time, unsatisfactory scarring, asymmetry and/or unacceptable cosmetic result.

Risks associated with tumescent anesthesia (lidocaine and epinephrine) include blurred vision, mental/mood changes, drowsiness, dizziness, unusually slow heartbeat, rash, itching, swelling, anxiety, apprehensiveness, restlessness, tremor, weakness, sweating, palpitations, pallor, nausea and vomiting, headache, and respiratory difficulties.

Risks associated with punch biopsy may include bleeding, bruising, pain, infection, or damage to the structures beneath the biopsy site (such as artery or nerve).

Subjects using drugs that reduce coagulation (aspirin or NSAIDs) may experience increased bruising or bleeding at the treatment site. Any other medications prescribed for the procedure or after-procedure by the investigator have their own risks; these risks should be discussed with the subject.

Apyx Medical Corporation

Protocol Number: APX-21-04

Effective Date: March 19, 2024

Revision No: 7.0

Title: Histological Evaluation of Human Skin Biopsies to Assess the Effects of Renuvion APR Treatment as an Adjunct Procedure in Facelift Surgery

A grounding pad is used to ground/neutralize the electrical current. Subjects undergoing radiofrequency treatment will be kept away from contact with metal parts which are grounded, or which have appreciable capacitance to earth.

As the Investigator will be treating the subjects per their Standard Practice of Care, there may be additional risks associated with the facelift procedure. The Investigator will be responsible for properly reviewing all potential risks with the patient prior to treatment

Any unexpected or unforeseen complications will be managed by the investigator throughout the conduct of the study. Unforeseen or unexpected side effects not listed above will be reported to the sponsor and regulatory representatives (IRB) as they occur.

#### 2.2.1.1 MINIMIZATION OF POTENTIAL RISKS

These risks are mitigated by utilizing qualified clinical Investigators who have training and are experienced in facelift procedures and Renuvion procedures. In addition, risks are mitigated by including only those subjects that meet the study eligibility criteria.

#### 2.2.2 POTENTIAL BENEFITS

This study is being conducted to determine if there are histological indicators of skin quality demonstrating improvement following the use of the Renuvion APR system.

### 3. STUDY PURPOSE

The purpose of this study is to gather quantifiable data on Renuvion's impact on skin elasticity and hydration, indicators of skin quality and estimate the biological skin age using DNA methylation.

### 4. STUDY DESIGN AND ENDPOINTS

#### 4.1 DESCRIPTION OF THE STUDY DESIGN

This study is a prospective, single-arm clinical study to be conducted at up to three clinical sites in the US. Up to 10 subjects will be enrolled and treated if they meet the inclusion/exclusion criteria and provide written informed consent.

Enrolled subjects meeting all entrance criteria and confirmed eligible for study treatment will be asked to participate. Subjects will receive a lower facelift surgery per the Investigator's standard clinical practice and treatment with the Renuvion APR System. The mid/upper-face area will not be treated with Renuvion and the lower face/neck area will be treated with Renuvion. Treatment will consist of subdermal coagulation of soft tissue using the Renuvion APR handpiece.

Standardized images will be taken prior to treatment and during each follow-up visit using the site's camera system. Baseline assessments and pre-treatment images should be obtained within 30 days of the study treatment.

 Apyx Medical Corporation	
Protocol Number: APX-21-04	Effective Date: March 19, 2024 Revision No: 7.0
Title: Histological Evaluation of Human Skin Biopsies to Assess the Effects of Renuvion APR Treatment as an Adjunct Procedure in Facelift Surgery	

## 4.2 DURATION OF STUDY

Recruitment for this study may take approximately 4-6 months. Following the treatment visit, subjects will be followed for a total duration of 180-days. Therefore, the anticipated total duration of the study is approximately 12 months.

## 4.3 STUDY OUTCOME MEASURES

1. Change in histology evaluation of biopsy tissue between the untreated portion of the face and the Renuvion treated portion at the D180 visit and compared to baseline.
2. Analysis of all adverse events through the D180 follow-up visit.
3. Analysis of bruising post-procedure.
4. Analysis of swelling post-procedure.
5. Healing profile.
6. Analysis of bleeding during surgery.
7. The Principal Investigator will complete a PGAIS assessing overall aesthetic improvement in the treatment area at day 45, 90, and 180 post-treatment.
8. The subject will complete a SGAIS assessing overall aesthetic improvement in the treatment area at day 45, 90, and 180 post-treatment.
9. The subject will complete a Patient Satisfaction Questionnaire (PSQ) at the 180-day follow-up visit.
10. Change in estimated biological skin age from baseline to D180.

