#### 4.3.4.1 HISTOLOGY EVALUATION OF BIOPSY TISSUE

Tissue samples will be assessed via microscopy, histology, and immunohistochemistry for biological markers of elasticity (collagen density, elastin, fibrillin-1) and hydration (HA) at Baseline and Day 180.

[figure not shown]
The density of dermal collagen is an indicator of skin elasticity because of collagen's role in maintaining the strength of the skin, helping it to resist mechanical deformation. Other biological markers of elasticity are fibrillin-1, a glycoprotein that supports the integrity of the dermal elastic fiber network, and elastin, an essential protein of the elastic fibers of the skin, such as oxytalan and elaunin. Well-studied biological markers of skin hydration include aquaporin-3 (AQP3), water- and glycerol-transporting membrane proteins expressed in the epidermis and glycosaminoglycans (GAGs), which are linear polysaccharide molecules, including HA, that bind water and help regulate the hydration of the dermis.

Two living human skin tissue samples will be collected at baseline during the facelift procedure prior to any treatment with the Renuvion APR system and at Day 180 post-surgery (D180) during the follow up visit. Skin punch biopsies ranging from 3-5 mm in diameter will be obtained from left side of the face. One tissue sample will be taken from the untreated portion of the face within 2cm of the Root of the Helix and 2cm of the hairline. Measures should be taken to ensure the biopsy is taken from facial skin, rather than scalp skin. The second tissue sample will be obtained from cheek skin in the untreated area of the lower face within 2 cm of the treatment line. See **Figure 3**. Both biopsies will be taken prior to any treatment with the Renuvion APR System at Baseline and then again after treatment at the same locations at D180. The untreated skin tissue samples from non-surgical sites for each subject will be provided as control specimen. The tissue samples will be fixed in 10% neutral buffered formalin and prepared for histological and immunohistochemical assessments. In brief, tissues will be gross-trimmed, dehydrated, oriented

 Apyx Medical Corporation	
Protocol Number: APX-21-04	Effective Date: March 19, 2024 Revision No: 7.0
Title: Histological Evaluation of Human Skin Biopsies to Assess the Effects of Renuvion APR Treatment as an Adjunct Procedure in Facelift Surgery	

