### 7.4.4 FOLLOW-UP

Subjects will be asked to return to the clinic for follow-up visits at 1, 2 (optional), 7, 14, 45, 90, and 180 days post-treatment. At all visits, subjects will be assessed for safety and adverse events, healing progress, and protocol deviations. Standardized images will be completed at Day 7, 45, 90, and 180. At 45, 90, and 180-days post procedure study outcome measures (GAIS) will be completed. At the 180-day follow-up appointment the subject will complete a PSQ and punch biopsies will be taken as described in **Section 4.3.4.1**; confirm only acute NSAID use (a maximum 2-3 doses allowed), if applicable, in the prior 2 weeks.

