### 7.4.7 END OF STUDY (COMPLETION)

All subjects who have signed an Informed Consent Form will be considered enrolled in the study. Subjects who complete the study duration will be considered to have completed the study. The end of study will be defined as completion of all study visits by all enrolled subjects. If a device-related AE, SAE, or unanticipated serious device-

 APYX™ MEDICAL Apyx Medical Corporation	
Protocol Number: APX-21-04	Effective Date: March 19, 2024 Revision No: 7.0
Title: Histological Evaluation of Human Skin Biopsies to Assess the Effects of Renuvion APR Treatment as an Adjunct Procedure in Facelift Surgery	

related effect is ongoing at the final study visit, the subject will be followed until resolution, until the condition stabilizes, until the event is otherwise explained, or the subject is lost to follow-up.

A study closure visit may be conducted at the study site in order to review record retention requirements, device disposition requirements, etc., with site personnel. The Sponsor may choose to conduct the closure visit via telephone contact if appropriate.

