Study investigators are provided liberty to mitigate adverse events as deemed necessary per IHC GCP Guidelines E6(R2)4.3.2 which states “During and following a subject’s participation in a trial, the investigator/institution should ensure that adequate medical care is provided to a subject for any adverse events related to the trial”.

Adverse event resolution dates will be determined by investigator using either in-person or remote (phone, video call, text, email, etc.) examinations or communication with the subject. To ensure the most accurate reporting of adverse event durations, investigators are instructed not to wait until scheduled office follow-up visits to assess resolution.

It is the Investigator’s responsibility to determine seriousness, severity, and relatedness of the Adverse Event to the device and procedure using the definitions in this protocol.

The PI will record all reportable events with start dates occurring any time after informed consent is obtained until 7 (for non-serious AEs) or 30 days (for SAEs) after the last day of study participation. At each study visit, the investigator will inquire about the occurrence of ETES/AEs/SAEs since the last visit. Events will be followed for outcome information until resolution or stabilization.

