### 10.2 SAMPLE SIZE

The study will include up to 10 treated subjects from up to three (3) U.S. sites.

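### Up to half of the facial punch biopsies are taken at the last scheduled visit with no later safety contact, and the adverse-event windows disagree on whether later events count

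*Combined protocol and SAP*

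**What the plan says.** - **Biopsies.** Section 4.3.4.1 takes two samples on each of two occasions. For the first pair: "Both biopsies will be taken prior to any treatment with the Renuvion APR System at Baseline". The second pair comes from those same two sites, 180 days on. Section 7.4.4 places that second pair at the final visit: "At the 180-day follow-up appointment the subject will complete a PSQ and punch biopsies will be taken".
- **Named risks.** Section 2.2.1: "Risks associated with punch biopsy may include bleeding, bruising, pain, infection, or damage to the structures beneath the biopsy site". It gives artery and nerve as examples of those structures.
- **Schedule.** Sections 7.3.2 and 7.4.4 and Table 3 list visits at Days 1, 2 (optional), 7, 14, 45, 90 and 180, and nothing later. Section 4.2 gives 180 days of follow-up in total. Section 7.4.7: "The end of study will be defined as completion of all study visits by all enrolled subjects".
- **Questioning.** Section 8.3 ties the AE interview to study visits, and Table 3 does the same for AE and healing assessments.
- **Recording window.** Section 8.3 has the investigator record events from consent "until 7 (for non-serious AEs) or 30 days (for SAEs) after the last day of study participation". Section 8.4.1 records them from first device exposure only to the last follow-up visit.
- **Analysis window.** Outcome measure 2, in section 4.3 and again in the synopsis, is "Analysis of all adverse events through the D180 follow-up visit".
- **Continued follow-up.** Sections 7.4.7 and 8.4.1 extend follow-up for listed events that are ongoing at the final visit. Separately, 8.3 requires any unresolved event to be followed at intervals of 7 days or less until it resolves or stabilises.

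**The concern.** The Day 0 wounds are looked at repeatedly after they are made; the D180 wounds have no scheduled look afterwards. Infection, haematoma or a nerve symptom can appear days after a punch, when no one is due to ask.

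Two things are at stake. First, delayed events from the second pair of biopsies will tend to be under-counted relative to the first pair, because one pair is actively queried and the other relies on self-report. Second, even a reported event has an uncertain place: one section records it, another does not, and the outcome measure excludes it. Sites could follow different sections, and the AE tables would then depend on which section each site read.

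The D180 biopsies also carry information that the Day 0 pair cannot. The Day 0 punches are made during a facelift, so bleeding, bruising or infection there is hard to separate from the surgery. The D180 punches have no concurrent surgery. The documents give them no purpose other than the study's histology and methylation outcomes.

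**Working it through.** **Inputs.** Section 10.2: "The study will include up to 10 treated subjects from up to three (3) U.S. sites". Section 4.3.4.1: two biopsies at Day 0 and two at D180. Section 5.5.2: withdrawn subjects are not replaced. The plan gives no dropout rate and no biopsy complication rate, so both are treated as assumptions. Section 10 gives no power calculation, so there is no planned figure to reproduce.

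**1. Share of biopsies at the last scheduled visit.** With N = 10 treated and C completing D180, share = 2C / (2N + 2C).

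| C (assumed) | D180 biopsies | All biopsies | Share |
|---|---|---|---|
| 10 | 20 | 40 | 50% |
| 9 | 18 | 38 | 47% |
| 8 | 16 | 36 | 44% |
| 7 | 14 | 34 | 41% |

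**2. Scheduled observation after each pair.** Day 0 pair: six required visits (Days 1, 7, 14, 45, 90, 180) plus optional Day 2, ending 165 to 195 days later under the D180 visit window. D180 pair: no later visits, 0 days.

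**3. One event traced through the rules.** Take a non-serious biopsy-site infection starting four days after the D180 visit, and assume participation ends at that visit, since the plan does not define its last day.

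| Rule | Where | Result |
|---|---|---|
| Scheduled questioning | 8.3, Table 3 | Not asked about |
| Recording to 7/30 days | 8.3 | Recorded, if the site hears of it |
| Recording to last visit | 8.4.1 | Not recorded |
| AE outcome to D180 | 4.3, synopsis | Not analysed |
| Follow-up of events ongoing at final visit | 7.4.7, 8.4.1 | Does not apply: not yet started |
| Follow-up of unresolved events | 8.3 | Applies once known |

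A serious event starting 20 days after D180 gives the same column, because it lies inside the 30-day limit of 8.3.

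**4. Could it matter with so few biopsies?** For an assumed per-biopsy rate p of a delayed event, independent across 20 biopsies, P(at least one) = 1 − (1 − p)^20. This gives 18% at p = 1%, 33% at 2%, 64% at 5% and 88% at 10%. The documents support no particular p; the range shows only that an event is not far-fetched.

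**The case against.** The strongest reply is that capture after D180 is passive, not absent. Section 8.3 keeps recording open for 7 or 30 days. Subjects are told in the consent form, in take-home instructions and verbally to report complications promptly. Unscheduled visits are allowed at any time (7.4.6). Once an event is known, 8.3 requires contact every 7 days or sooner, and that rule is limited neither to device-related events nor to events ongoing at the final visit. This all stands. A reader might infer that the D180 biopsies get no follow-up, or that a subject with a late complication would be left unfollowed; the documents support neither. The gap is in asking and in counting.

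Three further limits also stand:

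- The order of procedures within the D180 visit is not given, so the biopsies cannot be called the last act of the study. AE assessment is scheduled that day, and immediate bleeding or pain could be recorded then.
- A reader might infer that the study will publish a distorted biopsy safety profile. No outcome measure reports biopsy safety separately; the effect is on the all-AE outcome.
- It is not stated how a biopsy event would be attributed. Section 8.2.2 judges device and procedure together, so such an event cannot be assumed to be classed as unrelated.

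The consent pages are not available for review, so any biopsy aftercare wording there cannot be judged. None of this supplies a scheduled contact after D180 or resolves the conflict between 8.3, 8.4.1 and outcome measure 2.

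**Conclusion.** The point holds as a gap in elicitation combined with a contradiction in windows. Two of each subject's four biopsies, at most 20 of 40, are made at a visit after which nothing is scheduled. A delayed complication is captured only by self-report and lies outside outcome measure 2 even when reported. Half is a ceiling that needs all 10 subjects treated and completing D180; with 7 to 9 completers the share is 41% to 47%.

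The conclusion assumes that participation ends at the D180 visit and that outcome measure 2 means what it says about its end point. The size of any under-count cannot be estimated, because the plan gives no complication rate. The study is small and descriptive, so this does not threaten the histology results. It should be corrected because it affects the completeness of the safety data and is cheap to put right.

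**What to change.** Apply the window that 8.3 already states, everywhere:

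1. **8.4.1:** replace the last-visit end of recording with the 7-day (non-serious) and 30-day (serious) limits, and define the last day of participation from which they run.
2. **Outcome measure 2, in both 4.3 and the synopsis:** include events starting within those limits after D180.
3. **Table 3 and 7.4.4:** add a scheduled remote safety contact by telephone or video, modes that 8.3 already uses, at the end of the window: one at 7 days for all events and one at 30 days for serious events.
4. **4.2 and 7.4.7:** extend the 180-day total to cover the contact, and define end of study to include it. State whether it counts as the final visit for the IRB completion notice in 13.2, which is due within 30 days of that visit.

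The planned share of D180 biopsies with a later safety check goes from 0 of 20 to 20 of 20 at full completion. Treatment, sample size and the histology outcomes are unchanged.

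The cost is an amendment and at most 2 × 10 = 20 short calls by existing staff. Last-subject completion moves about 30 days later. With the 4 to 6 months of recruitment in 4.2 and about 6 months of follow-up, the total becomes roughly 11 to 13 months, so the 12-month estimate should be rechecked.

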### 4.3.1 EVALUATION TOOLS

The following evaluation tools will be used in this study:

#### 4.3.4.1 HISTOLOGY EVALUATION OF BIOPSY TISSUE

Tissue samples will be assessed via microscopy, histology, and immunohistochemistry for biological markers of elasticity (collagen density, elastin, fibrillin-1) and hydration (HA) at Baseline and Day 180.

[figure not shown]
The density of dermal collagen is an indicator of skin elasticity because of collagen's role in maintaining the strength of the skin, helping it to resist mechanical deformation. Other biological markers of elasticity are fibrillin-1, a glycoprotein that supports the integrity of the dermal elastic fiber network, and elastin, an essential protein of the elastic fibers of the skin, such as oxytalan and elaunin. Well-studied biological markers of skin hydration include aquaporin-3 (AQP3), water- and glycerol-transporting membrane proteins expressed in the epidermis and glycosaminoglycans (GAGs), which are linear polysaccharide molecules, including HA, that bind water and help regulate the hydration of the dermis.

Two living human skin tissue samples will be collected at baseline during the facelift procedure prior to any treatment with the Renuvion APR system and at Day 180 post-surgery (D180) during the follow up visit. Skin punch biopsies ranging from 3-5 mm in diameter will be obtained from left side of the face. One tissue sample will be taken from the untreated portion of the face within 2cm of the Root of the Helix and 2cm of the hairline. Measures should be taken to ensure the biopsy is taken from facial skin, rather than scalp skin. The second tissue sample will be obtained from cheek skin in the untreated area of the lower face within 2 cm of the treatment line. See **Figure 3**. Both biopsies will be taken prior to any treatment with the Renuvion APR System at Baseline and then again after treatment at the same locations at D180. The untreated skin tissue samples from non-surgical sites for each subject will be provided as control specimen. The tissue samples will be fixed in 10% neutral buffered formalin and prepared for histological and immunohistochemical assessments. In brief, tissues will be gross-trimmed, dehydrated, oriented

 Apyx Medical Corporation	
Protocol Number: APX-21-04	Effective Date: March 19, 2024 Revision No: 7.0
Title: Histological Evaluation of Human Skin Biopsies to Assess the Effects of Renuvion APR Treatment as an Adjunct Procedure in Facelift Surgery	

and embedded in paraffin, and histology slides of sectioned tissue at 3-5 mm will be prepared. All slides will be stained for hematoxylin and eosin (H&E), trichrome, Verhoeff Van 21Gieson stain. Expression of biological markers will be assessed by immunohistochemistry (IHC) at two timepoints. The collected samples at baseline and D180 will be stained for elastin and fibrillin-1. Histopathological evaluation and the integrity of the dermal elastin and collagen fibers will be assessed and semi-quantitatively scored via light microscopy by a board-certified pathologist. Additional staining may be needed at the discretion of the pathologist.

FIGURE 3: BIOPSY LOCATIONS

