#### 1. RP-18032301: Evaluation of Porcine Skin Tissue Epidermal Temperature During Subdermal J-Plasma (Renuvion) Application (Non-GLP)

This was a pre-clinical study in which the Renuvion system was used to coagulate the subdermal tissue of porcine skin at various treatment parameters in order to measure the maximum temperature on the surface of the epidermis. In this study, the maximum recorded epidermal surface temperatures were 39.1°C and 40.2°C. These temperatures were recorded after performing six consecutive passes of the Renuvion system under the same area of tissue. Six consecutive passes under the same tissue was included in the study to represent a “worst case” scenario. Six passes are not commonly performed clinically. However, even in this “worst case” scenario the epidermal surface temperature remained within safe limits. Pedroso, et.al, reported that because of superficial thermal safety concerns, the skin surface temperature should be maintained below 45°C. This study was subsequently published. The summary of the published study is as follows:

*J-Plasma helium was used in porcine, liver, kidney and muscle tissue at 20%, 50% and 100% power and 1 L/min and 3 L/min gas flow at 1, 5, and 10 second intervals. J-Plasma was then used in ovarian and uterine tissue at maximum power and gas flow settings in intervals of 1, 5, 10 and 30 seconds. Concluded that J-Plasma has predictable thermal spread in a variety of tissue types. Thermal depth of spread increased linearly with increased power setting, gas flow rate, and exposure time. Even at settings that greatly exceeded the manufacturer’s recommendation, the depth of thermal spread associated with the J-Plasma device was less than 3 mm (regardless of the type of tissue) and the diameter of lateral spread was 12 mm or less.*

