## 7.2 STUDY PROCEDURE

The lower facelift surgery will be performed as per the investigator's standard clinical practice. The Renuvion APR System treatment will be performed using 4 treatment passes with settings of 80% and 1.5 LPM of helium flow with an activation speed of approximately 1-3cm/s. See **Section 4.3.4.1** for detailed instructions regarding collection, storage, and shipment of punch biopsy tissue samples. For all subjects the Renuvion APR System will be used in open surgery between the skin and SMAS on the neck, submentum, and lower facial skin flap. The mid/upper-face area will not be treated with Renuvion. A video or photograph of the face after the biopsies will be taken prior to Renuvion treatment to ensure proper location of punch biopsies at the D180 visit.

Procedure data and adverse events will be captured.

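### Section 4.3.4.1 places the second biopsy in untreated lower-face skin, contradicting Outcome 1 and the protocol's description of the treated area

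*Combined protocol and SAP*

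**What the plan says.** Outcome 1 (Section 4.3, with the same wording in the synopsis) is a histology contrast "between the untreated portion of the face and the Renuvion treated portion at the D180 visit and compared to baseline". It needs one Day 180 sample from skin that received Renuvion and one from skin that did not, each with a baseline sample.

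Section 4.3.4.1 is the only running text that defines the sites:

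- Sample 1 is "taken from the untreated portion of the face within 2cm of the Root of the Helix" and close to the hairline.
- Sample 2 is "obtained from cheek skin in the untreated area of the lower face within 2 cm of the treatment line".
- Both are taken before any Renuvion at baseline, "then again after treatment at the same locations at D180".
- The section points to Figure 3, captioned as the biopsy locations. The figure is missing from the copy reviewed here.

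On what is treated, Section 4.1 says the mid and upper face is not treated and "the lower face/neck area will be treated with Renuvion". The synopsis agrees. Section 7.2 names the neck, the submentum and the lower facial skin flap. It also says: "A video or photograph of the face after the biopsies will be taken prior to Renuvion treatment", so that the sites can be found again at Day 180.

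**The concern.** Section 4.3.4.1 uses the same adjective, *untreated*, for both sites and then sends the investigator back to the same two places at Day 180. Followed as written, the arm of the contrast that Outcome 1 calls treated is empty. It also conflicts with Sections 4.1 and 7.2, where the lower face is the treated region.

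The histology outcome is listed first and matches the title of the study. No outcome is formally labelled primary, but Section 7.3.2 calls the Day 180 visit the primary endpoint. The DNA methylation outcome (Outcome 10, Section 4.3.4.8) is run on tissue left over from the same biopsies, so a misplaced sample affects both outcomes. If some lower-face samples come from skin that Renuvion did not reach, a small or absent difference cannot be told apart from a sampling error. With up to three sites applying the sentence, different readings are a practical risk.

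**Working it through.** The plan gives no alpha, power, effect size or standard deviation, and Section 10.1 specifies descriptive statistics only. There is no planned figure to reproduce. The check is a count, a comparison of passages, and one line of algebra.

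**Inputs**

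- Sites per subject: 2 (Section 4.3.4.1)
- Timepoints: 2, baseline and Day 180 (Section 4.3.4.1 and the table of study procedures)
- Treated subjects: up to 10 (Section 10.2)

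**Step 1: count the samples.** 2 sites × 2 timepoints × 10 subjects = 40 biopsies at most, or 10 in each site-by-time cell.

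| Cell | Samples | Renuvion-treated tissue? |
|---|---|---|
| Baseline, both sites | 20 | No, on any reading |
| Day 180, upper site | 10 | No, on any reading |
| Day 180, lower-face site | 10 | Depends on how *untreated* is read |

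On the literal reading the last cell contributes 0, so 0 of 40 samples are treated tissue. If the lower-face site lies inside the treated area, it contributes 10 of 40, which gives one treated-versus-untreated pair per subject at Day 180. Outcome 1 needs the second case.

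**Step 2: test the two readings of *untreated*.**

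- *Never treated.* This is how the word is used for sample 1 in the same paragraph. It makes Section 4.3.4.1 contradict Outcome 1 and leaves no treated sample.
- *Not yet treated at baseline.* This fits Outcome 1 and Section 4.1. But the baseline timing is stated separately, and every site is untreated at that moment, so the word would add nothing. Being within 2 cm of a line also names no side of it. The phrase about the lower face points to the treated side, but the sentence does not say so, and Section 7.2's lower facial skin flap is a narrower description than Section 4.1's lower face.

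**Step 3: look for another safeguard.** The Section 7.2 image is taken before Renuvion is applied. It serves to relocate the biopsy and cannot show what was treated afterwards. Section 7.2 says procedure data are captured but does not say whether the extent of treatment is among them. Figure 3 may show the site.

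**Step 4: size of the dilution.** Let δ be the mean device effect in correctly placed samples, and let m of 10 lower-face samples be untreated with no device effect. Then

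mean observed effect = [(10 − m)·δ + m·0] / 10 = δ·(1 − m/10).

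| m | Effect lost | Effect retained |
|---|---|---|
| 0 | 0% | 100% |
| 1 | 10% | 90% |
| 5 | 50% | 50% |
| 10 (literal reading) | 100% | 0% |

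The documents give no information on m.

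**The case against.** The best defence is that a treated sample was plainly intended. The sentences after the disputed one contrast collection before treatment with collection after it. The control is described as coming from non-surgical sites, which implies that the other sample is not a control. Sections 4.1 and 7.2 put the lower face in the treated region. The revision log says the version 7.0 change to this section was about when to collect samples, which fits a word meant to describe timing. Figure 3 may make the location obvious to every site. The Section 7.2 image does the job it was given, which is relocation.

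Most of this stands as evidence of intent. It makes the *not yet treated* reading plausible and means the side of the line is not a wholly open choice. It does not remove the contradiction: an investigator following the sentence can sample outside the treated area and still comply. If Figure 3 shows a treated site, the text is wrong against the figure.

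A reader might also try to size the problem from Section 2.1.2, where a published summary reports that "the diameter of lateral spread was 12 mm or less", and derive from it a safe distance or the share of the 2 cm zone with no thermal effect. The documents do not support that step. The tissues listed are liver, kidney, muscle, ovary and uterus, not skin. Exposures ran from 1 to 30 seconds, whereas Section 2.1 describes heating for 0.040 to 0.080 seconds and Section 7.2 a moving handpiece. Nothing says how samples would spread across the zone, or that acute thermal spread bounds histological change at Day 180.

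**Conclusion.** The concern holds as a contradiction in the current text. Section 4.3.4.1 cannot be followed literally and still deliver Outcome 1, and it disagrees with Sections 4.1 and 7.2 about the status of lower-face skin. Under the literal reading, 0 of up to 40 samples are treated tissue, against the up to 10 that Outcome 1 needs. Under the benign reading the side of the line is implied but not expressly stated.

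A reader might infer that the study will have no treated tissue at all. That is not shown: the rest of the protocol points to a treated sample being intended, and Figure 3 was not available. What is shown is an instruction that permits the wrong sample.

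The m/10 dilution assumes that misplaced samples carry no device effect and that correctly placed ones share a common mean effect. Since m is unknown, the range is 0% to 100%. The same tissue feeds the methylation outcome, so that outcome is exposed too. The point should be settled before more biopsies are taken, because the location of a collected Day 180 sample cannot be corrected afterwards.

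**What to change.** 1. Reconcile the synopsis, Sections 4.1, 4.3, 4.3.4.1 and 7.2, and Figure 3. Section 4.3.4.1 should state that the second site lies inside the area to be treated with Renuvion, so that its Day 180 sample is treated tissue, and that the control site lies outside that area.
2. Mark the treatment line on the skin before the Section 7.2 photograph or video, and record the area actually treated on the CRF.
3. If a minimum distance from the line is wanted, the sponsor should choose and justify it; the documents do not supply one.
4. For subjects already biopsied, classify each lower-face sample as treated, untreated or unverifiable before slides are read. Use operative records or other documentation of the treated area, since the pre-treatment image alone cannot settle it. Report the classification with the results.

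The cost is a wording amendment and one CRF field, with no extra biopsy. Samples found to be untreated or unverifiable leave the treated-site summary; with at most 10 subjects, each one removed is a tenth or more of that summary.
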